1- The training program has a positive impact on quality of life and functional autonomy in people with fibromyalgia.

2- The training program is effective and generates little fatigue.

3- The training program has a high adherence in people with fibromyalgia.

4- The hypoxia produced and the relative intensity of the program has a direct impact on the balance of oxidant/antioxidant levels.

5- The levels of TAS, MDA, liver enzymes, biochemical variables and hemogram remain stable without significant alterations.

6- Occlusive training in people with fibromyalgia proves to be an effective and safe therapy as part of the treatment.

Objectives

Main Objective

To improve the quality of life and functional autonomy.

Specific Objectives

- 1- To achieve results by minimizing the fatigue produced in people with fibromyalgia.

- 2- To get people accustomed to the adapted program and make it part of their routine.

- 3- To measure variables in blood/plasma to verify the results obtained for a better understanding of the disease and its impact.

- 4- To identify those blood/plasma variables most susceptible to occlusive training that will allow a better understanding of fibromyalgia disease.

- 5- To test the effectiveness and adherence of occlusive training in people with fibromyalgia by means of blood/plasma samples, functional tests and questionnaires.

- 6- To evaluate occlusive training as a valid physical complementary therapy for people with fibromyalgia.

Methodology

The methodology will be carried out by an experimental design research to test the effect of the independent variable on the dependent variable. In this case, the independent variable will be the pressure exerted by the occlusive cuff on the thigh musculature during the planning of aerobic exercise walking of low intensity and reduced time, and its impact on the dependent variable, which is determined by plasma and blood values, mitochondrial protein expression, standardized questionnaires of the impact of the disease (psychometric), and functional tests of physical condition (distances and times performed), which will be measured before and after the intervention period.

Study population

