The study population will be men and women diagnosed with fibromyalgia between 18 and 70 years of age from Seville capital and province. In this way, a more representative sample will be included, since both active and sedentary people will be included. There will also be people who are active at work and people who are engaged in housework.

Sample size.

With a 95% CI and a percentage of 1.8% prevalence of the disease in Andalusia for both sexes, according to data collected from the Ministry of Health and Family in the year 2021 of people affected by fibromyalgia with a precision of $\pm 3\%$, the sample size is $n=75$.

Inclusion and exclusion criteria

Criteria for inclusion in the research

- A patient meets diagnostic criteria for fibromyalgia if the following three conditions are present: (American Rheumatology Association). Wolfe et al., (2010).
 - o 1) Widespread Pain Index (WPI) ≥ 7 and Symptom Severity Score (SS Score) ≥ 5 or WPI 3-6 and SS ≥ 9 .
- Symptoms have been present, at a similar level, during the last three months.
- The patient has no other pathology that could explain the pain.
- Recent negative COVID-19 test.

Exclusion criteria

- Other associated pathologies that may hinder the development of the investigation.
- Mobility limitations.
- Injuries that add to those of the disease itself and hinder mobility.
- No medical evaluation of the diagnosis of the disease.
- Negative results in the inclusion tests.
- Cardiac pathologies.
- Blood pressure higher than 130-90 mmHg.
- No COVID-19 test.

Definition of variables

-Independent variables:

- Cuff pressure to produce occlusion.
- Walking time and intensity.

Dependent variables:

- Psychometric questionnaires of impact of fibromyalgia disease:
- Symptom severity index (Score).
- Widespread Pain Index (WPI).
- Fibromyalgia Impact Questionnaire (FIQ).
- Multidimensional Fatigue Inventory (MFI-20).
- Blood/plasma measurements.
- Biochemical values.
- Oxidative stress, total antioxidants and Coenzyme-Q values.
- Standardized physical fitness tests
 - Time up and Go test.
 - 30-second chair stand test (Cycles).
 - 6-minute walk test (distance covered).
 - Lower body dynamometer test (Newtons of force).
 - Hand press test (Newtons of force).

Data collection

Data collection will be based mainly on 3 stages.

Stage 1

Once the screening on inclusion and exclusion sections has been passed and carried out, the following should be done:

1. Standardized disease questionnaires.

- WPI
- SScore

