Descriptive statistics were calculated for each variable. The normality of the distribution of data was verified by the Shapiro-Wilk test. Variables showing skewed distributions were log-transformed to obtain a normal distribution. Relative changes within each group were assessed using a paired Student's t test. To compare baseline variables the Student's t test, standardized differences ($\pm 90\%$ confidence level) and qualitative differences were estimated. To detect between-group differences, multiple 2 x 2 (group x time) mixed-analysis of variance was performed and adjustments for multiple comparisons were made using the Bonferroni method by dividing the significance level of 0.050 by the number of comparisons, additionally standardized differences ($\pm 90\%$ CL) and qualitative differences were estimated. The effect size of standardized differences was determined by Cohen's d statistic, and the Hopkins' scale was used to determine the magnitude of the effect size, where 0 to 0.19 = trivial, 0.20 to 0.59 = small, 0.60 to 1.19 = moderate, 1.2 to 1.99 = large, and >2 = very large (Hopkins et al 2009). A practically worthwhile difference was assumed when the difference score was ≥ 0.2 of the between-subject SD. Qualitative assessment indicates the likelihood for the between-group differences to be substantial, referring to possible differences, to likely, to very likely, and to almost certain differences. The probability of a true difference between groups was qualitatively classified as almost certainly not: $<0.5\%$; very unlikely: 0.5% to 5%; unlikely: 5% to 25%; possible: 25% to 75%; likely: 75% to 95%; very likely: 95% to 99.5%; and almost certain: $>99.5\%$. A substantial effect was defined as $>75\%$ (Batterham and Hopkins 2006).

Functional tests

30-second chair stand test

Objectives: (Test No. 1)

1-To assess the strength of the extensor muscles of the knees and hips, responsible for gait failure and falls in 30 seconds.

2-To evaluate the resistance to loss of lower body strength, which causes early fatigue, in 30 seconds.

3- To evaluate the perceived effort and relative intensity of the patient's effort.

Bibliographic references. Validity and standardization

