 - Rest in a chair for 3-5 minutes without occlusion.
 - Before finishing the rest, re-set the pressure established for each participant.
- 3- Each participant will have to perform the training session with a surgical mask and the handling of the material will be with latex gloves that will be discarded after finishing the training session.
- 4- Each training session will be carried out with groups of 4 participants simultaneously.
- 5- Halfway through the intervention period, each participant's resting SBP will be measured again in order to make adjustments to the maguitar pressure.

Measurements for each session/participant (variables)

1- Before the beginning of each session:

- O2 saturation and resting heart rate.
 - Constants to check the safety of the beginning
- Motivation level (1-10) (additional information)
 - To be used as a subjective check of the patient in order to verify the weekly evolution and to anticipate solutions to possible complications of the volunteer (abandonment).
- Quality of sleep (very good, fairly good, fairly bad, very bad). Pittsburg Subjective Sleep Scale (additional information)
 - To be used as a subjective check of the patient with the aim of checking the weekly evolution and to anticipate solutions to possible complications of the volunteer (abandonment).
- Pain level (1-10) Visual Analog Pain Scale (VAS).

2- After each session:

- O2 saturation and heart rate
- Perceived intensity of exertion scale at the end of the modified Borg (1-10).
- Pain level (1-10) Visual Analog Pain Scale (VAS).

Timing of phases and weeks.

Phases:

- 1- Completion of questionnaire of criteria for inclusion in the research and items necessary to be part of it (to be carried out in the fibromyalgia association itself).
- 2- Blood sampling (to be carried out at the viamed hospital).
- 3- Previous evaluation of autonomy, quality of life and impact of the disease by means of questionnaires, tests and functional physical tests standardized for this purpose. It will be carried out at the Pablo de Olavide University facilities (CIRF).
- 4- Familiarization. It will be carried out at the Universidad Pablo de Olavide (CIRF) facilities.
- 5- Period of research intervention 9 weeks (18 supervised sessions). It will be carried out at viamed hospital. Pain Unit.
- 6- Final evaluation. It will be carried out in the facilities of Pablo de Olavide University (CIRF).

Weeks:

Week 1

- Monday: Pre-intervention blood sampling, disease impact questionnaires

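### Hypothesis 6 sets out to show the cuff training is safe, but the readable text describes no adverse-event definition, no reason entry for a stopped session or early cuff release, and no by-arm event summary

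*Combined protocol and SAP*

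**What the plan says.** Hypothesis 6 in the combined protocol and SAP reads: "Occlusive training in people with fibromyalgia proves to be an effective and safe therapy as part of the treatment". Hypothesis 5 is close to a laboratory-safety statement: "The levels of TAS, MDA, liver enzymes, biochemical variables and hemogram remain stable without significant alterations". Bloods are drawn before and after the programme, and both arms go through all research stages.

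Under Definition of variables, the dependent variables are the disease questionnaires (symptom severity score, WPI, FIQ, MFI-20), blood and plasma measures, and fitness tests. Cuff pressure and walking time and intensity are listed as independent variables. Adherence appears in Hypothesis 3 and specific objective 5.

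Stage 2 refers to a daily record sheet for each participant. The section on measurements for each session lists saturation and resting heart rate beforehand, labelled "Constants to check the safety of the beginning". It adds motivation and sleep, kept partly "to anticipate solutions to possible complications of the volunteer (abandonment"), and pain. Afterwards it lists saturation, heart rate, Borg exertion and pain.

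The preventive measures are exclusion of cardiac disease and raised blood pressure, supervised sessions, a pain ceiling for cuff pressure, and a mid-programme blood pressure re-check.

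Statistical analysis gives descriptive statistics for each variable, paired t tests and a group-by-time comparison: "To detect between-group differences, multiple 2 x 2 (group x time) mixed-analysis of variance was performed". It names no safety or tolerability summary.

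**The concern.** A claim of safety needs data that could contradict it directly. For walking under blood flow restriction, the most direct data are symptoms during or after a session, a session cut short, and a cuff deflated early, each with its reason. The readable text gives no place for any of these and does not say how they would be summarised.

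If the plan is followed as described, the word safe would rest on indirect measures. Bloods in weeks 1 and 13 cannot show dizziness or numbness in week 5. Pain is rated before and after each session, whereas the pain ceiling under Familiarization applies throughout, so a breach during inflation would go unseen. Participants place the cuff and re-set the pressure themselves, so early release is a practical possibility.

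A supervisor may well notice such an event. Without an entry, though, it does not become data, and what was not collected cannot be recovered at analysis.

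**Working it through.** **The plan's own figure.** No figure in the plan concerns safety. Its one sample-size figure reproduces: 1.96² × 0.018 × 0.982 / 0.03² = 75.4, against 75 stated. It addresses the precision of a prevalence estimate and has no bearing on harms.

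**Where an event could be recorded.**

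| Place in the plan | What is listed | Event, early release or stopped session, with reason? |
|---|---|---|
| Dependent variables | Questionnaires, bloods, fitness tests | No |
| Independent variables | Cuff pressure; walking time and intensity | Named, but not said to be logged as delivered or with a reason for deviation |
| Before each session | Saturation, heart rate, motivation, sleep, pain (5) | No |
| After each session | Saturation, heart rate, Borg, pain (4) | No |
| Statistical analysis | Descriptives, t tests, mixed ANOVA, magnitude-based inference | No by-arm event summary |

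The per-session count is 0 of 5 + 4 = 9 measurements. Taking saturation and heart rate as one item each time makes it 0 of 4 + 3 = 7.

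**Sessions affected.** The plan gives 18 sessions in the list of phases and 20 in Stage 2.
- Cuff arm: 7 × 18 = 126 to 7 × 20 = 140. Early cuff release can occur only here.
- Comparison arm: 6 × 18 = 108 to 6 × 20 = 120. Symptoms and stopped sessions can occur here too.

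**What full recording could show.** This is a separate question from the recording gap and bears only on the wording of Hypothesis 6. With zero events in n participants, the exact upper limit on the per-participant rate is 1 − α^(1/n), with α = 0.05 for a one-sided 95% limit and 0.025 for a two-sided 95% interval.
- n = 7 (cuff): 1 − 0.05^(1/7) = 34.8%; 1 − 0.025^(1/7) = 41.0%.
- n = 6 (no cuff): 1 − 0.05^(1/6) = 39.3%; 1 − 0.025^(1/6) = 45.9%.

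The documents give no expected event rate. For assumed true rates of 1%, 5%, 10% and 20%, the chance of at least one event among 7, 1 − (1 − p)^7, is 6.8%, 30.2%, 52.2% and 79.0%. An event with a true rate of 5% per participant would therefore go unseen about 70% of the time (100 − 30.2 = 69.8%).

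**The case against.** Several points on the other side carry weight.

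- **Harm-relevant data are collected.** A flare in pain or fatigue should register in FIQ, WPI, the symptom severity score, MFI-20 or post-session Borg, and Hypothesis 2 on low fatigue is in effect a tolerability hypothesis. This stands, and it rules out the reading that the plan collects no safety data. These measures still do not record a discrete event or why a session ended.
- **Walking time and cuff pressure are named variables.** A stopped session is a shortened walk and an early release is a fall in pressure, and descriptive statistics are promised for each variable. This narrows the gap. It does not close it, because the text does not say that either is logged as delivered or with a reason.
- **The daily sheet is not shown.** It may already have a line for events, and some front pages are not available to this review. This stands as a limit: the point covers what the readable text describes.
- **The study may be finished.** Statistical analysis is in the past tense and Participants' arms gives realised numbers, although parts of that section use the future tense. If sessions are complete, no recording can be added.
- **It is only a hypothesis, and no objective names safety.** True, but a hypothesis worded this way invites the conclusion, and 7 participants cannot support it.

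A reader might go further and infer that events happened and were left out, or that the fall from 37 participants at baseline to 13 reflects intolerance of the cuff. The documents support neither. They attribute the reduction to exclusion phases and do not say whether any of the other 37 − 13 = 24 had begun sessions.

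**Conclusion.** The point holds as a limited one. The readable text has no adverse-event definition, no entry for a stopped session or early cuff release with its reason, and no event summary by arm. Harm could show only indirectly. None of the 9 listed per-session measurements fills this gap, across 126 to 140 planned cuff sessions and 108 to 120 without the cuff.

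Separately, no result in 7 cuff participants could justify the safety wording of Hypothesis 6: zero events leaves an upper limit of 34.8% one-sided or 41.0% two-sided. That limit assumes independent participants with a common event rate, all 7 fully observed. It measures what the sample leaves open and is not an estimate of how often harm occurs.

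The conclusion on recording depends on the daily sheet having no events line, which cannot be checked here. The conclusion on wording does not depend on that, nor on whether sessions are complete. The change should be made; confidence is medium.

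**What to change.** 1. If sessions are still running and the daily sheet has no such line, add one in both arms: any symptom during this session or since the last, and whether the session was stopped early, with the reason. In the cuff arm only, add early cuff release with the reason. State whether the mid-session rest is with or without occlusion, since the text describes it both ways and a planned deflation must be distinguishable from an unplanned one.
2. Report by arm the number of participants with at least one event, with exact (Clopper-Pearson) limits, among everyone who started at least one session. With 7 and 6 participants, make no between-arm test.
3. In any case, restate Hypothesis 6 as a description of tolerability in the cuff arm with its upper limit.
4. If sessions are complete, restate Hypothesis 6 and, unless the sheet already had an events line, disclose that events were not systematically asked about.

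The cost is one line per session on a sheet already kept, with no extra visits, and a weaker safety statement. If sessions are complete, only wording changes.

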- Wednesday: Familiarization 1 and functional tests nº 1,2 and 3
- Friday: Familiarization 2 and functional test nº 4

Week 2

- Monday: Familiarization 2 (material and training)
- Friday: Familiarization 2 (material and training)

Week 3 to week 12 (intervention period)

- Tuesday: Intervention period Intervention
- Friday: Intervention period

Week 13 Final evaluation.

- Monday: Post-intervention blood sampling, disease impact questionnaires
- Wednesday: Familiarization 1 and functional tests 1, 2 and 3.
- Friday: Functional test nº 4

Participants' arms.

Participants were divided into 2 non-randomized groups with a total of 37 participants at baseline and overcoming the different phases of exclusion 13.

- **Intervention group:** This group will perform each of the above research stages and perform the occlusive cuff intervention period. n= 7 participants.
- **Non-intervention group:** This group will perform each of the above research stages and will perform the intervention period without the occlusive cuff. n= 6 participants.

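### The only sample-size statement (n=75) is a prevalence-survey calculation that supports none of the planned tests, and no size or precision is restated for the 7 vs 6 participants in the arms

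*Combined protocol and SAP*

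**What the plan says.** The Sample size section of the combined protocol and SAP is one sentence. It begins "With a 95% CI and a percentage of 1.8% prevalence of the disease in Andalusia for both sexes", gives a precision of ±3% and concludes n=75. The section just before it states: "The study population will be men and women diagnosed with fibromyalgia between 18 and 70 years of age".

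The Statistical analysis section plans two kinds of test. Within groups: "Relative changes within each group were assessed using a paired" Student's t test. Between groups: "To detect between-group differences, multiple 2 x 2 (group x time) mixed-analysis of variance was performed", with 0.05 divided by the number of comparisons, which is not given. It adds standardized differences with 90% limits and a magnitude-based reading. "A practically worthwhile difference was assumed when the difference score was" at least 0.2 of the between-subject SD. "Qualitative assessment indicates the likelihood for the between-group differences to be substantial", and an effect counts as substantial above 75%.

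The Participants' arms section, at the end of the document, reports: "Participants were divided into 2 non-randomized groups with a total of 37 participants at baseline and overcoming the different phases of exclusion 13". For the cuff arm it says: "This group will perform each of the above research stages and perform the occlusive cuff intervention period. n= 7 participants". The arm without the cuff has 6.

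**The concern.** A sample-size section should show that the study can answer its question with useful precision. This one answers a different question, namely how many people to survey to estimate how common fibromyalgia is. It names no outcome, effect, SD, power, number of groups or allowance for loss.

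The number is also not the number studied. The documents move from 75 to 37 to 13 without explanation, do not say whether 7 and 6 are starters or completers, and give no size or precision for 7 vs 6.

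What is at stake is how the hypotheses will be read. Hypotheses 1 and 6 claim benefit, and Hypothesis 6 is worded as proof of effectiveness and safety. Hypothesis 5 expects laboratory values to stay stable, which a non-significant test would seem to confirm. With n=75 standing as the stated size, a reader could give these conclusions more weight than 13 people can carry.

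**Working it through.** **1. The plan's own figure.** Inputs from the Sample size section: z = 1.96 (95%), p = 0.018, d = 0.03.

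n = z² p(1−p) / d² = 1.96² × 0.018 × 0.982 / 0.03² = 0.067904 / 0.0009 = 75.45.

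The stated 75 is reproduced (strict rounding up gives 76, which is immaterial). This identifies the method. None of its inputs enters the precision of a t test or a mixed ANOVA.

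**2. Group comparison at 7 vs 6.** In a 2 x 2 mixed ANOVA the group x time test equals a two-sample t test on change scores, here with 7 + 6 − 2 = 11 df. The documents give no power, SD or number of comparisons. Assumed: 80% power, two-sided 0.05 before Bonferroni, effects in SDs of the change score.

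- SE = √(1/7 + 1/6) = 0.556 change-score SD.
- Detectable difference (noncentral t): 1.71 change-score SD. For 75 split 38/37 it would be 0.66.
- 90% half-width = t(0.95, 11 df) × SE = 1.796 × 0.556 = 1.00 change-score SD.

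**3. Paired tests.** Same assumptions: 1.27 change-score SD with n=7 (6 df) and 1.43 with n=6 (5 df).

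**4. Conversion to the plan's unit.** The 0.2 threshold is in between-subject SD. With equal pre and post variances and pre-post correlation r, one change-score SD equals √(2(1−r)) between-subject SD. The documents give no r, so a range is shown.

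| Assumed r | Factor | Detectable difference | 90% half-width | Plan's threshold |
|---|---|---|---|---|
| 0.5 | 1.000 | 1.71 | 1.00 | 0.2 |
| 0.7 | 0.775 | 1.33 | 0.77 | 0.2 |
| 0.9 | 0.447 | 0.77 | 0.45 | 0.2 |

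At every r shown, the half-width is more than twice the worthwhile difference.

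**5. Secondary and conditional: the 75% rule.** The Statistical analysis section does not say how the probability is computed. Suppose it means P(true difference > 0.2 SD) > 0.75 from a t distribution on 11 df. The observed difference must then exceed 0.2 + 0.697 × SE. With SE = 0.556/0.431/0.249 between-subject SD, that is 0.59/0.50/0.37. Each value is smaller than its 90% half-width (1.00/0.77/0.45), so the interval would still include zero. Simulating no true effect, with the SE estimated and the 0.2 threshold fixed, about 30%/26%/14% of comparisons are called substantial in one direction or the other. As written, the Bonferroni step divides the significance level; nothing applies it to this rule.

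**The case against.** The best reply is that no planned test uses n=75, that the arms section openly states 37, 13, 7 and 6, and that 90% limits are already planned, so imprecision will show with each result. This stands in part. The counts are disclosed and the intervals will help. What remains is a stated justification that justifies nothing in the study, three unreconciled numbers, and hypotheses worded as if the size sufficed. The arms section is partly in the past tense, so recruitment may be over; that limits the remedy to reporting and conclusions.

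Four stronger readings are tempting, and the documents do not support them:

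- **That the comparison can detect only very large differences.** The plan's own scale calls 1.2 to 1.99 large and above 2 very large. Before Bonferroni, 1.71/1.33/0.77 between-subject SD is large, large and moderate.
- **That effectiveness cannot be shown at all at this size.** A true difference of 1.71 change-score SD has 80% power under the assumptions above. What is supported is low power for smaller effects. Separately, non-randomized allocation limits causal claims at any sample size.
- **That the 75% rule has a known false-positive rate.** The rates depend on a computation that the plan does not spell out. If the probability were taken against zero instead of 0.2, the null rate would be about 50% (25% in each direction) at every r. The plan also introduces these estimates as an addition to the ANOVA and does not say that the label alone establishes effectiveness.
- **That the 24 people between 37 and 13 dropped out.** The text attributes the reduction to phases of exclusion and says nothing more.

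**Conclusion.** The sample-size statement is wrong as written. The arithmetic is sound but its target is a prevalence that a study of diagnosed patients cannot estimate, so n=75 justifies neither the group x time comparison nor the paired tests. That conclusion needs no assumption.

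The scale of the consequence does rest on assumptions: 80% power, two-sided 0.05 before Bonferroni, and r from 0.5 to 0.9. Within that range the imprecision is substantial throughout, and any Bonferroni division would raise the detectable difference further. The figures for the 75% rule are weaker evidence because they hold only under one reading of it.

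Two consequences for interpretation follow. A non-significant result at 7 vs 6 is evidence neither of no effect (Hypotheses 1 and 6) nor of stability (Hypothesis 5). And seven cuff users are too few to support a conclusion that safety is proven.

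**What to change.** In a dated amendment:

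1. State that n=75 is a prevalence-precision figure and does not justify the group comparison or the paired tests. Keep it on record.
2. Reconcile 75, 37 and 13 (7 vs 6), and say whether 7 and 6 are starters or completers.
3. State the expected 90% half-width at 7 vs 6, with its unit and assumptions, as achieved precision and not as a prospective justification.
4. Report Hypotheses 1, 5 and 6 as effect estimates with intervals. Say that a non-significant result does not show absence of effect or stability, that a label above 75% does not by itself establish effectiveness, and that non-randomized allocation also limits causal claims.
5. Do not conclude that safety is proven. Summarise descriptively the laboratory, saturation, heart-rate and pain data already collected.

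Cost: the stated size becomes less favourable and the conclusions more limited, with a little extra reporting. No patients are added and no planned test changes.

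### The single-step Bonferroni adjustment of the between-group tests can be replaced by Holm's procedure on the same family: a free but modest gain in power

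*Combined protocol and SAP*

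**What the plan says.** The Statistical analysis section plans one mixed model per variable: "To detect between-group differences, multiple 2 x 2 (group x time) mixed-analysis of variance was performed". For these tests, "adjustments for multiple comparisons were made using the Bonferroni method by dividing the significance level of 0.050 by the number of comparisons". The number is not given. Nor does the section say whether comparisons are outcomes or contrasts within one ANOVA. No testing order, hierarchy or stepwise rule appears anywhere.

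The Main Objective is stated as "To improve the quality of life and functional autonomy", but no primary outcome is named. Under Definition of variables, the dependent variables are:

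- "Psychometric questionnaires of impact of fibromyalgia disease": four instruments (symptom severity, WPI, FIQ, MFI-20).
- Blood measures: general biochemistry, not itemised there, and "Oxidative stress, total antioxidants and Coenzyme-Q values".
- "Standardized physical fitness tests": five tests.

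The Functional tests section adds a Modified Shuttle Walk test. The Participants' arms section gives two non-randomised groups of 7 and 6.

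**The concern.** Single-step Bonferroni holds every test to the strictest threshold, even after some hypotheses have been rejected. Holm relaxes the threshold after each rejection and keeps the same error guarantee, so Bonferroni gives up rejections for nothing in return. Its usual advantage is that it yields matching simultaneous confidence intervals. That does not apply here: the plan reports 90% limits and says nothing of adjusting them.

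With 13 participants and a dozen or more outcomes, the threshold could be very small, and avoidable loss of power is worth removing. The undefined divisor adds to this, because the reader cannot tell which threshold any result was held to.

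**Working it through.** **The plan's own figures.** The plan gives no divisor, per-comparison level or power, so there is nothing on this point to reproduce. Its one computed design figure is the sample size: 1.96² × 0.018 × 0.982 / 0.03² = 75.45, which matches the stated 75. That is a prevalence-precision calculation and does not bear on group comparisons.

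**Per-comparison level.** Level = 0.05/m, with m counted from Definition of variables.

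| Reading of the family | m | Level |
|---|---|---|
| 4 questionnaires + 5 fitness tests + 3 oxidative/antioxidant/coenzyme measures | 12 | 0.00417 |
| Same, with biochemistry counted once | 13 | 0.00385 |
| Same, with the shuttle walk | 14 | 0.00357 |
| Contrasts within one ANOVA (assumed 2 to 4) | 2–4 | 0.025–0.0125 |

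A 2 × 2 design has one group × time interaction per outcome. An adjustment of those interactions therefore makes most sense across outcomes, but the text does not say so.

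**Power under Bonferroni, m = 12.** The group × time test is equivalent to a two-sample t-test on change scores. With 7 and 6 participants there are 11 degrees of freedom, and the noncentrality is d × √(7×6/13) = 1.797d, where d is the difference in SDs of change. Two-sided testing is assumed, and the values of d are assumptions because the plan gives no target effect. The critical t at 0.00417 is 3.600.

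- d = 1.2: noncentrality 2.157, power 13.8%
- d = 1.5: noncentrality 2.696, power 25.7%
- d = 2.0: noncentrality 3.595, power 52.7%

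**Holm on the same 12 tests.** Order the p-values. Compare the smallest with 0.05/12, the next with 0.05/11, and so on to 0.05/1, stopping at the first failure. The first step equals the Bonferroni threshold and later steps are looser, so whatever Bonferroni rejects, Holm rejects too.

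The gain was simulated with 20,000 runs per case and between-outcome correlations of 0 and 0.5. Average power is taken over the outcomes that truly differ.

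| Truth | Bonferroni | Holm |
|---|---|---|
| All 12 differ by 1.5 SD | about 26% | 31–34% |
| Six differ by 2.0 SD | about 53% | about 58% |
| Four differ by 1.2 SD | about 14% | under 1 point more |

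In the two cases with some true nulls, Holm's family-wise error stayed at or below 0.04.

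**What Holm cannot repair.** Even at an unadjusted 0.05 (critical t 2.201), power is 26.0% at d = 0.8 and 50.3% at d = 1.2.

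**Cost of giving the main-objective outcomes priority.** Take 2 main outcomes and 10 others.

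- *Two separate families, each by Holm at 0.05.* If no outcome truly differs and outcomes are independent, the chance of at least one false positive is 1 − 0.975² × 0.995¹⁰ = 0.096. Simulation gave 9.5%, 8.9% and 7.9% at correlations 0, 0.3 and 0.5. Bonferroni over all 12 gave 4.8%, 4.6% and 4.1%.
- *Gating.* In a separate simulation with 13 outcomes at correlation 0.3, the others were tested only if a single main outcome succeeded. Power per later outcome fell from 13.3% to 11.3% when all differed by 1.2 SD. It fell from 13.2% to 2.0% when the main outcome differed by only 0.2 SD and the others by 1.2 SD.

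**The case against.** The strongest case for leaving the plan alone is that Bonferroni is valid, that Holm's first step is no looser, and that the useful gains need half or all of the outcomes to differ by 1.5 to 2.0 SD. In a sparser, smaller-effect case the gain is under 1 point. The limits that matter most are 13 participants and non-random allocation, and no multiplicity procedure changes either. All of this stands and sets the size of the point. None of it is a reason to prefer Bonferroni, since Holm is never worse on the same family.

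A reader might infer two stronger points that the documents do not support.

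- *That the plan splits 0.05 equally over every outcome, so the main-objective outcomes are tested at 0.004.* The divisor and the family are not stated. If only contrasts within each ANOVA are meant, outcomes are not adjusted for each other at all.
- *That testing the main-objective outcomes first recovers power at no cost.* Two outcomes tested at 0.025 would have power of 37% at 1.2 SD and 56% at 1.5 SD, against 14% and 26%. That gain comes from picking two outcomes, which the plan does not do. Its general considerations tie all the functional tests to functional autonomy. A main-objective family on those terms has about eight or nine members, so the first-step level is 0.0063 to 0.0056 and power at 1.5 SD is 30–32%. Priority also costs study-wide error or power on later outcomes, as shown in the working.

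Timing is a further obstacle. The analysis section is in the past tense and final group sizes are already reported, so choosing primary outcomes now may be post hoc. Replacing Bonferroni with Holm selects no outcome and is less exposed to that criticism, provided it is disclosed.

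**Conclusion.** The point holds as a small improvement without a statistical downside. Holm dominates single-step Bonferroni on any fixed family with more than one test, whatever the divisor, and that part needs no assumption about effects or correlation. The size of the gain does: at 7 and 6 participants with 12 outcomes it runs from under 1 to about 8 percentage points of average power across the cases examined. The level of about 0.004 holds only if the family is the listed outcomes. The change does not make the trial adequately powered and does nothing about confounding from non-random allocation. Priority for a short list of outcomes is a trade-off for the investigators to weigh.

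**What to change.** In the Statistical analysis section, replace the Bonferroni sentence with one that:

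1. defines the family as the group × time tests of a listed set of outcomes and states how many there are;
2. applies Holm's step-down procedure to that family at an overall two-sided 0.05.

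This costs two sentences, with no new data and no burden on participants. If results have already been compared by arm, the change should be reported as made afterwards, with the Bonferroni results alongside.

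Optionally, the investigators may name a short list of Main Objective outcomes to be tested first, but only if the list is fixed before results are compared by arm. The plan must then state the price: study-wide error of roughly 8% to 9.5% when no outcome differs if two families (2 and 10 outcomes) each use 0.05, or lower power for later outcomes if they are gated.
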